6.3 PATIENTS SETS ANALYSED

The following analysis sets will be defined for this trial:

- Enrolled set (ENR)

This patient set includes all patients with informed consent given. The enrolled set will be used for patient disposition tables.

- Treated set (TS)

This patient set includes all patients who are documented to have received and taken at least one dose of any study medication during the treatment cycles (from day 1).

Proprietary confidential information © 2017 Boehringer Ingelheim International GmbH or one or more of its affiliated companies

The TS will be used for all planned safety and efficacy analyses.

- **MTD Set (MS)**

The MTD set defines the set of patients in the first part of the trial that are fully evaluable for determination of the MTD in the first treatment course. The MTD set will be used for some safety analyses in the first part, this is specified in the technical TSAP.

Patients in the TS who were replaced within the MTD evaluation period in the first part of the trial will be excluded from the determination of the MTD. Replacement of patients in the first part of the study is defined in Section 3.3.4.3 of the CTP. The final list of replaced patients is supplied by the Trial Clinical Monitor (TCM) no later than the last report planning meeting before the database lock for the safety analysis.

6.5 POOLING OF CENTRES

This section is not applicable because there are no inferential statistics, and therefore there is no statistical model in which centre/country can be included.

Proprietary confidential information © 2017 Boehringer Ingelheim International GmbH or one or more of its affiliated companies

6.6 HANDLING OF MISSING DATA AND OUTLIERS

In general, missing data will not be imputed, unless required for the following analyses and definitions. Then the rules as described below apply.

Missing dates that affect the evaluation of endpoints specified in previous sections of this TSAP will be imputed utilising a “worst case” approach, which will be applied on a case-by-case basis (depending on the affected endpoint) and agreed to by the trial team members at the final BRPM before database lock at the latest.

The rules in the table 6.6: 1 below have been agreed by the trial and project teams, and will be used in this trial, if applicable.

Table 5.3.2.2:1 Rules for imputations of missing or incomplete dates

Date	Imputation rule
Date of birth	In case only the year is given: 1 st of January
Date of death	Date last known to be alive. If only year and month are given: this will be imputed with 1 st of the month for the analysis of OS
Date of first histological diagnosis	1 st of month if day is missing 1 st of January if month also missing
Date of start of concomitant medication	No imputation required
Date of end of concomitant medication	No imputation required
Date of start of subsequent anti-cancer therapy (imputation required only for censoring of PFS)	If the day (respectively day and month) of the start date of subsequent anti-cancer therapy is missing, then the first of the month (respectively 1st January) will be imputed unless this date leads to a date before the stop date of study medications. In this case, the study medications stop date + 1 day will be imputed. Additionally, all imputed start dates of subsequent anti-cancer therapy should be before death date if available.
Date of stop of subsequent anti-cancer therapy	No imputation required
Date of end of treatment (only for patients still ongoing at time of snapshot/DBL)	Date of snapshot If date of death before this date, use date of death

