#### 7.3.2 Secondary analyses

Disease control (CR, PR or SD), time to objective response, duration of objective response, will be summarized using descriptive statistics. Kaplan-Meier curves will be plotted to graphically display the progression-free survival and overall survival for the expansion cohort in Part B.

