5.2.2.2 Second part

Time to OR

Time to objective response is defined as the time from first treatment administration until first documented CR or PR.

Time to objective response will only be calculated for patients with an objective response:

- Time to OR [days] = date of first documented CR or PR - date of first treatment administration + 1.

Duration of OR

Duration of objective response is defined as the time from first documented CR or PR until the earliest of disease progression or death among patients with objective response.

Duration of objective response will only be calculated for patients with an objective response. For patients with disease progression or death:

- Duration of objective response [days] = date of outcome – date of first assessment indicating OR + 1.

For patients without disease progression or death:

- Duration of objective response (censored) [days] = date of outcome – date of first assessment indicating objective response + 1

The censoring rules for duration of OR are given in Table 5.2.2.2: 1.

Table 5.2.2.2: 1 Derivation rules for Duration of Objective Response

Situation	Outcome (event or censored)	Date of outcome
No other anti-cancer therapy		
Alive and not progressed, no more than one consecutively missed radiological assessments	Censored	Date of last radiological assessment
Alive and not progressed, two or more consecutively missed radiological assessments	Censored	Date of last radiological assessment prior to missed radiological assessments
Progressed, zero or one missed radiological assessment prior to progression	Event	Date of radiological assessment of progression
Progressed, but two or more consecutively missed radiological assessments prior to progression	Censored	Date of last radiological assessment prior to missed assessments

Proprietary confidential information © 2017 Boehringer Ingelheim International GmbH or one or more of its affiliated companies

Table 5.2.2.2: 1 Derivation rules for Duration of Objective Response (cont.)

Situation	Outcome (event or censored)	Date of outcome
Death but no progression, zero or one missed radiological assessment prior to death	Event	Date of death
Death without progression, but two or more consecutively missed radiological assessments prior to death	Censored	Date of last radiological assessment prior to missed assessments
Initiation of subsequent anti-cancer therapy		

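### The OS rule for a death date known only to the month has no floor at the date last known alive, so it can place death before a documented contact

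*SAP*

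**What the plan says.** The death row of the imputation table in SAP section 6.6 has two sentences and begins "Date last known to be alive. If only year and month are given: this will be imputed with". The second sentence in full is "If only year and month are given: this will be imputed with 1 st of the month for the analysis of OS". Neither sentence says that the later of the two dates is to be taken.

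The same table does set a lower limit for another date. A partial start date of subsequent anti-cancer therapy goes to the first of the month or year "unless this date leads to a date before the stop date of study medications", in which case the day after the stop date is used.

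Above the table, a general clause says that missing dates bearing on endpoints "will be imputed utilising a “worst case” approach, which will be applied on a case-by-case basis (depending on the affected endpoint"), with agreement by the trial team at the final report planning meeting before database lock. The table rules are then introduced as agreed and to be used where applicable.

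OS enters the analysis through Protocol section 7.3.2: "Kaplan-Meier curves will be plotted to graphically display the progression-free survival and overall survival for the expansion cohort in Part B". Protocol section 6.2.3.3 has Part B patients followed for survival every 90 days (± 15), by telephone if needed. Protocol section 7.2 plans no formal tests.

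**The concern.** A month-only death date is most likely when a death is learned of at a distance, as can happen with quarterly telephone contacts. The first of the month is the earliest date consistent with the month alone. It is not always consistent with the rest of the record: if the patient was seen, dosed or scanned later in that month, the imputed death comes before a day on which the patient is documented alive.

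The row is also awkward internally. If its first sentence is the rule for a wholly missing date, a patient last seen on 20 June with no death date is given 20 June, while the same patient with death recorded as June is given 1 June. Knowing more produces an earlier and impossible date. At stake is a small error, always towards shorter survival, in the Part B OS curve.

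**Working it through.** The plan states no figure for the effect of this rule, so there is nothing to reproduce. The rule can be enumerated over a calendar.

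**Inputs.** From SAP 6.6: the death date becomes the first of the month. From SAP section 7: months = days × 12 / 365.25. Assumed: a 365-day year, every death day equally likely, and a gap *g* from last contact to death that is uniform over 0 to *G* − 1 days. *G* = 7 mimics weekly treatment visits, *G* = 28 one treatment course, and *G* = 90 the observation-period interval.

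**Understatement under the current rule.** A death on day *d* of the month is moved back *d* − 1 days. Over the year the sum is 7 × 465 + 4 × 435 + 378 = 5373, for the 31-day months, the 30-day months and February. The mean is 5373 / 365 = 14.7 days (14.7 × 12 / 365.25 = 0.48 months). The maximum is 30 days (0.99 months).

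**Share of impossible dates.** The imputed date precedes the last contact when *g* < *d* − 1. For a given *d* that is min(*d* − 1, *G*) of the *G* possible gaps, so the share is the sum of min(*d* − 1, *G*) over the year, divided by 365 × *G*:

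- *G* = 7: 2219 / 2555 = 0.868
- *G* = 28: 5348 / 10220 = 0.523
- *G* = 90: 5373 / 32850 = 0.164

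**Understatement with a floor.** With the later of the first of the month and the last contact, the understatement is min(*d* − 1, *g*). The table gives averages per affected patient.

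| Assumed gap (days) | Impossible dates | Days before contact, when impossible | Understatement now | With floor | Due to missing floor |
|---|---|---|---|---|---|
| 0–6 | 87% | 13.8 | 14.7 | 2.7 | 12.0 |
| 0–27 | 52% | 10.5 | 14.7 | 9.2 | 5.5 |
| 0–89 | 16% | 10.5 | 14.7 | 13.0 | 1.7 |

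The last column also equals the second times the third: 0.523 × 10.5 = 5.5 and 0.164 × 10.5 = 1.7.

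**Example with assumed dates.** First dose 9 January, last contact 20 June, death recorded as June, in a non-leap year. The count is inclusive, as in the SAP's other time formulas, because the OS formula itself is not visible. The current rule gives 144 days (4.73 months). With the floor it is 163 days (5.36 months). The difference is 19 days.

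**Size on the curve.** With 18 Part B patients and no earlier censoring, each death lowers the curve by 1/18, or 5.6 percentage points. One affected date moves one such step to the left by at most 30 days.

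**The case against.** The best defence is that the SAP chooses a worst-case approach on purpose, and that an early death date is the conservative direction for a single-arm survival curve. That justifies the first of the month when no later contact exists. It does not justify a date on which the patient is known to have been alive, because the worst case must still be possible.

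A second defence is that the planning meeting before database lock could catch an impossible sequence. It could, but no such check is written for this row, and the row as written gives the impossible date.

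Third, most of the 14.7 days comes from the first-of-month convention, which the fix keeps. This stands. For the 90-day contact interval, where partial dates are most plausible, the floor recovers only about 1.7 days on average.

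Fourth, the OS and PFS derivations are not in the visible SAP text, so a floor may be stated there. This also stands. The first sentence of the death row may even be a second row label broken by the PDF reading, though neither reading supplies a floor.

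A reader might also infer that the rule shortens duration of response and PFS. Death is indeed an event for duration of response: SAP section 5.2.2.2 states "Duration of objective response is defined as the time from first documented CR or PR until the earliest of disease progression or death", and its derivation table counts as an event the situation "Death but no progression, zero or one missed radiological assessment prior to death". But the first-of-month rule is expressly limited to OS and no visible text carries it over. For those endpoints a partial death date falls under the general case-by-case clause. A reader might likewise infer that a wrong death date spreads to censoring through the subsequent-therapy row, which asks for imputed therapy starts to precede death. That would need both dates to be partial in one patient, and an OS-only imputed date to be reused there. The SAP does not say that it is.

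**Conclusion.** The point holds for OS only. In the visible text, a death date known to year and month is set to the first of the month with no floor at the date last known alive. The imputed death therefore precedes the last contact whenever that contact falls on day 2 or later of the month of death.

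About 52% or 16% of affected dates would be impossible for assumed uniform gaps of 0–27 or 0–89 days. The part of the understatement caused by the missing floor is about 5.5 or 1.7 days per affected patient, out of 14.7. These figures rest on uniform death days and assumed gaps; the documents give neither the gaps nor the number of partial dates.

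The consequence is minor. Few of 18 patients are likely to be affected, OS is shown descriptively without a test, and objective response, the Part B primary endpoint, does not use the date of death in this way. The documents do not support a claim that this rule distorts duration of response, PFS or their censoring dates. The conclusion is also subject to the unseen OS derivation.

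**What to change.** In the death row of the SAP 6.6 table, state that when only year and month are known, the date for OS is the later of the first of that month and the date last known to be alive. If the OS derivation outside the visible text already has this floor, a cross-reference in the row is enough.

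It would help to add a sentence saying whether the same rule or the case-by-case clause governs partial death dates for duration of response and PFS, so that nobody carries the OS rule over by default.

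The cost is one clause in the SAP and one line of code. No new data are needed, and the descriptive nature of the analysis does not change.

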\*\*\* End Of Treatment (EOT) visit must be performed within 14 days of the last administration of study drug, i.e. both Xentuzumab (BI 836845) and afatinib. If last administration of the study drug occurs during a scheduled visit, examinations as defined for EOT should be performed instead of examinations for the scheduled visit.

\*\*\*\*First Follow-up (FU) visit 42 calendar days (up to +7 days) after the last administration of study drug for all patients (part A and part B). Additional FU visits (only for patients who discontinue not due to progressive disease) at 8-week intervals until progression, lost to follow-up or initiation of other anti-cancer treatment.

\*\*\*\*\* Observation period only for part B. For details see [Section 6.2.3.3](#).

Written informed consent must be obtained before any trial specific screening assessments are performed.

In/Exclusion criteria must be checked at screening and ensured before study medication has been firstly administered.

 Physical examination: includes cardiopulmonary examination, examination of the regional lymph nodes, and examination of the abdomen and an assessment of the mental and neurological status.

Vital signs: include pulse, temperature and blood pressure.

 ECG to be performed at Screening/ pre-infusion, during infusion (after 30±5 mins) and immediately prior to the end of the infusion (-10 mins) on Day 1 of Course 1/ a single ECG to be taken on Day 15 of Course 1/ thereafter a single ECG to be taken pre-infusion at the start of every course on Day 1, and also at EOTV.

MUGA scan or echocardiogram not older than 28 days prior to start of treatment. Further scans may be performed post treatment if clinically indicated

Haematology, biochemistry and coagulation parameters. Safety labs may be collected up to two days prior to the scheduled time points. Safety lab result at course 1 visit 1 should be reviewed by investigator before first administration of study medications. From course 2 onwards, safety lab assessment will be done at visit 1 and 3 of each course. For details see [Section 5.2.3](#).

Urinalysis (Dipstick).

 For observation period (after the patient completed last follow-up and when progression occurred or when new anti-cancer therapy started), the investigator may report SAE if she/he becomes aware of and considers relevant.

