5.1.2 Second part

Objective response (OR)

The primary endpoint for the second part of the study is objective response (OR).

OR is defined as best overall response of complete response (CR) or partial response (PR). Best overall response to trial medication will be determined according to Response Evaluation Criteria In Solid Tumours (RECIST) version 1.1 (see Appendix 10.5 of the CTP) recorded from first administration of trial medication until the earliest of disease progression, death or last adequate tumour assessment before start of subsequent anti-cancer therapy.

Note that an adequate tumour assessment includes an assessment of target lesions, as well as radiological tests to evaluate non-target lesions and to search for new lesions, i.e. a RECIST tumour evaluation. If no RECIST tumour evaluation has been performed, the assessment will be set to missing.

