Subsequent anti-cancer therapy started before progression or death, no more than one consecutively missed radiological assessments prior to start of subsequent anti-cancer therapy	Censored	Date of last radiological assessment before initiation of subsequent anti-cancer therapy

Only radiological assessments after first assessment indicating objective response will be taken into consideration.

Disease control (DC)

DC is defined as best overall response of CR or PR or SD where best overall response is defined according to RECIST version 1.1 (see Appendix 10.5 of the CTP) from first administration of trial medication until the earliest of disease progression, death or last evaluable tumour assessment before start of subsequent anti-cancer therapy.

Note that an adequate tumour assessment includes an assessment of target lesions, as well as radiological tests to evaluate non-target lesions and to search for new lesions, i.e. a RECIST tumour evaluation. If no RECIST tumour evaluation has been performed, the assessment will be set to missing.

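### A partly missing start date of new anti-cancer therapy has no floor at a documented progression, so a patient who stops study drug before progressing can have that progression censored

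*SAP*

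**What the plan says.** The date-imputation table in SAP 6.6 has a row for the start of subsequent anti-cancer therapy. If the day is missing, or the day and month, "the first of the month (respectively 1st January) will be imputed unless this date leads to a date before the stop date" of study medication. "In this case, the study medications stop date + 1 day will be imputed". The only upper limit is that "all imputed start dates of subsequent anti-cancer therapy should be before death date if available". The row is labelled "imputation required only for censoring of PFS". The text introducing the table says its rules will be used in this trial where applicable.

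The paragraph before that sets a general principle: "Missing dates that affect the evaluation of endpoints specified in previous sections of this TSAP will be imputed" on a worst-case basis, case by case, agreed before database lock.

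The start date of new therapy is used in three visible places:
- **Duration of response** (SAP 5.2.2.2, Table 5.2.2.2: 1). If new therapy precedes progression or death, the patient is censored at the "Date of last radiological assessment before initiation of subsequent anti-cancer therapy".
- **Objective response** (SAP 5.1.2). The window for best overall response can close at the "last adequate tumour assessment before start of subsequent anti-cancer therapy".
- **Disease control** (SAP 5.2.2.2). The window is defined in nearly the same way.

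The derivation rules for PFS are not in the public text.

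On imaging, the protocol (Flow Chart footnotes and 3.1) does not allow treatment beyond progression. It continues to scan patients who stopped for other reasons "at 8-week intervals until progression, lost to follow-up or initiation of other anti-cancer treatment".

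**The concern.** The rule picks the earliest day the record allows and checks it only against the end of study treatment. For a patient who came off both drugs before progressing, the end of treatment says nothing about whether the switch came before or after progression. The protocol scan does: imaging is meant to stop at progression or at new therapy, so a protocol scan in the month of the switch is evidence that the switch had not yet happened. The rule ignores it and can reverse the true order.

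At stake is a real progression recorded as a censored time. The censoring is informative, because it falls on patients who have just progressed. It also lengthens estimated PFS and response duration, so it is not a worst case for either endpoint, although the same SAP section adopts that principle.

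**Working it through.** **Plan's own figures.** Protocol 7.6 gives probabilities of 73% and 86% for at least 3 responses in 18 patients at true rates of 20% and 25%. The exact binomial gives 0.7287 and 0.8647, so both reproduce. Neither depends on this rule.

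**The rule as coded.** Let F be the 1st of the known month, or 1 January if the month is missing. Let S be the study-medication stop date, read here as the last administration. The imputed start is F, or S + 1 if F is earlier than S. A progression on date P is displaced when the imputed start is earlier than P.

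**Who is protected.** If S is on or after P, there are two cases:
- F is before S: the imputed start is S + 1, which is after P.
- F is on or after S: the imputed start is on or after P.

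No progression is displaced in either case.

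**Who is exposed.** Suppose S is before P. The cases checked were 3 and 60 days before, with identical results. The documents give no gap g from progression to switch, so a range is assumed. With only the day missing, P is displaced when P and P + g share a calendar month and P is not on the 1st, which is L − g − 1 days in a month of L days (zero if negative). Over 2016 and 2017 (731 days: fourteen months of 31 days, eight of 30, one of 29, one of 28):

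| Assumed gap g | Day missing | Day and month missing |
|---|---|---|
| 7 days | (14×23 + 8×22 + 21 + 20)/731 = 539/731 = 73.7% | (358 + 357)/731 = 97.8% |
| 14 days | (14×16 + 8×15 + 14 + 13)/731 = 371/731 = 50.8% | (351 + 350)/731 = 95.9% |
| 21 days | (14×9 + 8×8 + 7 + 6)/731 = 203/731 = 27.8% | (344 + 343)/731 = 94.0% |
| 28 days | (14×2 + 8×1)/731 = 36/731 = 4.9% | (337 + 336)/731 = 92.1% |

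The last column uses the same formula with L = 366 and 365. These are shares of exposed patients with a partial date, not shares of the trial.

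**Dated example on the protocol schedule.**
- First dose 1 Sep 2016 (day 1). Partial response on 27 Oct (day 57), still present on 22 Dec (day 113).
- Both drugs stopped for an adverse event on 20 Jan 2017 (day 142). That is 142 − 113 = 29 days after the last scan, so the end-of-treatment scan is not optional (Flow Chart footnote 11). It is due by 3 Feb (day 156).
- Progression on 16 Feb (day 169). New therapy recorded as Feb 2017; true date 27 Feb.

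True duration of response by the SAP formula: 169 − 57 + 1 = 113 days, an event. The imputed switch is 1 Feb (day 154), before progression, so the patient is censored:
- End-of-treatment scan on 20 to 31 Jan (days 142 to 153), still in response: 142 − 57 + 1 = 86 to 153 − 57 + 1 = 97 days, censored.
- That scan missed, or done on 1 to 3 Feb: 113 − 57 + 1 = 57 days, censored.

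The event is lost in every variant. The time lost is 16 to 27 days with a January scan, and 56 days otherwise. Objective response does not change, because the response was already confirmed at day 113.

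**With the added floor.** The candidates are 1 Feb, 21 Jan and 17 Feb. The latest, 17 Feb, is imputed, and the progression counts as an event at 113 days.

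**The case against.** The strongest reply has five parts.

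1. **The stop-date floor covers the usual case.** Treatment ends at progression, so a patient who progresses on drug is safe. This stands. Harm needs a stop before progression, a later progression, a switch in the same month or year, and a partial date. The protocol asks for treatment dates at follow-up (6.2.3.2 and 6.2.3.3), and nothing shows how often they will be incomplete.

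2. **The row is limited to PFS by its own label.** PFS is a descriptive Kaplan-Meier curve for Part B (Protocol 7.3.2), not a listed endpoint, in a trial without formal tests. Its censoring table is not public, so the effect is inferred from the duration-of-response table. This also stands. But if the label is taken literally, duration of response, objective response and disease control depend on the same date with no tabulated rule.

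3. **Case-by-case review before database lock could catch the error, and response duration is shown per patient.** That is possible, but the table is introduced as the set of rules that will be used.

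4. **Worst case depends on the endpoint.** For objective response, an early switch can only remove scans, which is conservative. That is correct; the conflict is with PFS and response duration only.

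5. **A later floor may keep a scan taken after the true switch.** This is a real cost, dealt with in the fix.

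A reader might go further and infer that the primary endpoint is biased by the loss of a confirmatory scan. The documents do not support that: the row does not claim to govern objective response, and the example leaves it unchanged. Nor can one such case be called a quarter of the duration-of-response events. The protocol's 20% assumption gives 18 × 0.20 = 3.6 expected responders, which is not a count of events.

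**Conclusion.** The gap is real but narrow. For patients whose study-medication stop date precedes progression, the tabulated rule can place the start of new therapy before a documented progression. PFS, and duration of response if it uses the same date, are then censored instead of counted as events. This goes against the protocol's imaging rule and is not worst case for these endpoints. Patients whose stop date is on or after progression are unaffected.

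Among exposed patients with a partial date, the chance of displacement is high when the switch follows quickly or the month is missing. The number of such patients is unknown and, with about 18 in Part B, probably small. The effect is limited to descriptive endpoints. An effect on objective response is possible but not shown, and the sample-size figures do not change.

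The conclusion rests on three assumptions: that some start dates will be partial, which the SAP foresees; that PFS is censored at new therapy in the same way as duration of response; and that the stop date means the last administration. The third matters for a patient whose progression is found while both drugs are paused.

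**What to change.** Revise the row in SAP 6.6 so that the imputed start is the latest of:
- (a) the 1st of the known month, or 1 January if the month is missing;
- (b) the study-medication stop date plus one day;
- (c) the day after the last protocol tumour assessment in the known month or year, up to and including the first documented progression.

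Limb (c) must not pass the end of the known month or year. Limb (b) takes precedence over that cap if they conflict, for example when study drug stops on the last day of the month. The result must be before death.

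Replace the label limiting the row to PFS with a statement that it applies to PFS and duration of response. State explicitly whether the imputed date also closes the best-overall-response window for objective response and disease control.

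The cost is one row of text and minor programming, using data already collected. The downside is that a scan taken after the true switch in that month could be kept; list any patients for whom limb (c) sets the date so that this can be reviewed before database lock.
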